2.4.4 Analyses of efficacy endpoints

For statistics where international and conventional units do not impact the results (eg, means and least square (LS) means for percent changes from baseline, p-values for both percent and absolute changes from baseline, rates of patients below a threshold), derivations will be done and statistical models will be run using conventional units. For other statistics (eg, descriptive statistics at baseline and over time, absolute changes from baseline), derivations will be done with both international and conventional units.

Double-blind period

Statistical analyses for the primary and secondary efficacy endpoints will be conducted in the double-blind period and will compare each alirocumab dosing regimen group versus its contemporaneously randomized placebo group (ie, of the same dosing regimen cohort):

- alirocumab Q2W versus placebo Q2W
- alirocumab Q4W versus placebo Q4W

Of note, Q2W and Q4W refer to the dosing regimens initiated at randomization.

Efficacy endpoints analyzed with the ITT estimand will be analyzed in the ITT population. Efficacy endpoints analyzed with the on-treatment estimand will be analyzed in the mITT population.

OL period

With respect to efficacy data collected during the OL period, only descriptive summaries for each lipid parameter will be provided in the OL population.

Formal testing is not planned due to the absence of control group in the OL period.

Combined period (double-blind and OL periods)

For patients receiving alirocumab in the double-blind period, a combined summary including both the double-blind and open-label period assessments may be considered, referencing the double-blind baseline for variable calculations.

2.4.4.1 Analysis of primary efficacy endpoint

2.4.4.1.1 Primary efficacy analysis

Within each dosing regimen cohort, the percent change from baseline in LDL-C to Week 24 as defined in Section 2.1.3.1 will be analyzed in the ITT population using a mixed-effect model with repeated measures (MMRM) model. All post-baseline data available within Week 8 to Week 24 analysis windows will be used and missing data will be accounted for by the MMRM model.

For the Q2W dosing regimen cohort, the model will include the fixed categorical effects of treatment group (alirocumab, placebo), randomization strata (previous participation [yes or no] to DFI14223 study, baseline body weight [$<50 \text{ or } \ge 50 \text{ kg}$]), time point (Week 8, Week 12, Week 24), treatment-by-time point interaction, and strata-by-time point interaction, as well as the continuous fixed covariates of baseline LDL-C value and baseline value-by-time point interaction. Model assumptions for normality will be explored prior to the analysis testing.

For the Q4W dosing regimen cohort, the model will include the fixed categorical effects of treatment group (alirocumab, placebo), randomization strata (baseline body weight [<50 or ≥ 50 kg]), time point (Week 8, Week 12, Week 24), treatment-by-time point interaction, and strata-by-time point interaction, as well as the continuous fixed covariates of baseline LDL-C value and baseline value-by-time point interaction. Model assumptions for normality will be explored prior to the analysis testing.

Of note, the stratum related to the previous participation in the DFI14223 Phase 2 study will not be included in the model for the Q4W dosing regimen cohort, as too few patients from this Phase 2 study are enrolled in this cohort due to the late start of enrollment in the Q4W regimen.

These 2 separate models will be run using SAS Mixed procedure with an unstructured correlation matrix by treatment group (in case of convergence issue, a common unstructured correlation matrix for both groups will be used) to model the within-patient errors. Parameters will be estimated using restricted maximum likelihood method with the Newton-Raphson algorithm. Denominator degrees of freedom will be estimated using Satterthwaite's approximation. Throughout MMRM models, least-square (LS) mean and standard error (SE) at Week 24 will be provided for each treatment group within each dosing regimen cohort.

LS means difference at Week 24 will be provided for the comparison of each alirocumab dosing regimen group versus its contemporaneously randomized placebo group (ie, of the same dosing regimen cohort) as follows:

- alirocumab Q2W versus placebo Q2W
- alirocumab Q4W versus placebo Q4W,

with the SE, 97.5% confidence intervals (CI) and p-value, using appropriate contrasts. Statistical testing will be evaluated at a 2-sided significance level of 0.025 per comparison.

Within group least-squares means and standard errors will be provided, using weights equal to the observed proportion of patients in strata variable levels in the study population (ie, "population weight") rather than equal weights. Population weights are considered more appropriate than equal coefficients due to unbalances observed in the study population between levels of the randomization stratification factors.

Let $\mu 0$, $\mu 1$ be the population means of the percent change from baseline in calculated LDL-C at Week 24 under placebo and alirocumab in the Q2W dosing regimen cohort, and respectively $\mu 0'$, $\mu 1'$ the corresponding population means in the Q4W dosing regimen cohort. The hypotheses that will be tested are:

- For Q2W dosing regimen cohort: "H0: $\mu 0 = \mu 1$ versus "H1: $\mu 0 \neq \mu 1$
- For Q4W dosing regimen cohort: "H0: μ 0' = μ 1' versus "H1: μ 0' = μ 1'

The MMRM models relies on the "missing-at-random" (MAR) assumption. As we can never exclude the possibility for a not-missing-at-random (NMAR) missingness mechanism, sensitivity analyses to explore the impact of non-ignorable missingness on the primary efficacy analysis will be conducted (pattern mixture model approach using mixed imputation defined in Section 2.4.4.1.4).

2.4.4.1.2 Model assumption checks

Homogeneity of treatment effect across baseline LDL-C levels

In order to check the homogeneity of treatment effect versus baseline LDL-C, the following interaction terms will be added in the two primary MMRM models:

• Treatment group * baseline LDL-C.

• Treatment group * time-point * baseline LDL-C.

Within the framework of this model with interaction terms, for each dosing regimen cohort, a graph presenting the LS means difference versus the placebo group at Week 24 and the corresponding 97.5% CI will be provided by baseline LDL-C value.

Analysis of residuals:

The analysis of the residuals of the MMRM (for each dosing regimen cohort separately) will be primarily based on studentized residuals. It will include:

- Normality of studentized residuals, presented graphically using histogram and QQ-plot.
- Plot of studentized residuals versus predicted values.
- Distribution of studentized residuals, presented graphically using boxplots, within each category of the fixed categorical effects of the MMRM:
 - treatment group (alirocumab and placebo).
 - time point (Week 8, Week 12, Week 24).
 - treatment-by-time point interaction.
 - randomization strata.
 - randomization strata-by time point interaction.

2.4.4.1.3 Sensitivity to randomization strata

In order to assess the robustness of the primary analysis to randomization stratum mistakes (ie, the stratum recorded in IVRS differs from the actual one), the MMRM model for each dosing regimen cohort for the primary efficacy endpoint will be re-run including the actual stratum as per the eCRF instead of the stratum recorded in IVRS.

In addition, for each dosing regimen cohort, a sensitivity analysis excluding patients who previously participated in the Phase 2 DFI14223 study will be conducted for the primary efficacy endpoint.

2.4.4.1.4 Sensitivity to handling of missing data

Sensitivity analyses will be conducted to assess the robustness of primary efficacy analysis with regards to handling of missing data (7) (for each dosing regimen cohort separately).

Visual examination:

- In order to explore the missing data pattern, post-baseline LDL-C observations (in the ITT population) will be described by visit according to the following groups:
- 1. LDL-C available at Week 24* (ie, primary efficacy endpoint available),
- 2. LDL-C available at Week 12* but missing at Week 24*,

- 3. LDL-C available at Week 8* but missing from Week 12*,
- 4. LDL-C missing from Week 8

(*): as defined in Section 2.5.4 in Table 5

• Then, a graph of mean LDL-C levels (respectively percent change from baseline in LDL-C) ± SE at baseline, Week 8, Week 12 and Week 24 will be provided by missing data pattern, for each treatment group.

In the ITT population, demographic and baseline characteristics will be described within the missing data pattern number 1 versus the pooled others. P-values from Fisher exact test for categorical data and from asymptotic one-way ANOVA test for Wilcoxon scores (Kruskal-Wallis test) for continuous data, will be also provided, for descriptive purposes.

Multiple Imputations (under MAR assumption):

In addition to the MMRM method, for each dosing regimen cohort separately, the multiple imputation method will be used to address missing values, in the randomized population, followed by the testing of alirocumab versus placebo group, using an analysis of covariance (ANCOVA) model, with unequal variances by treatment group (except if convergence issue), with the intent to evaluate the robustness of the primary analysis using a different statistical method. The imputation model described in Section 2.4.4.2.2 will be used but without log transformation. In addition, for each simulation leading to negative imputed value, another value will be redrawn using MINIMUM option of MI SAS procedure.

Pattern mixture model (see Appendix C for more details)

For the Q2W dosing regimen cohort, multiple imputations will be used with different imputation strategies applied to LDL-C values missing during the on-treatment period (ie, within the time period from the first double-blind IMP injection up to the day of last double-blind injection +21 days) versus LDL-C values missing after treatment discontinuation (ie, after the day of last double-blind injection +21 days) based on the following assumptions:

- Patients within 21 days of their last double-blind IMP injection would continue to show benefit from treatment similar to that observed at the scheduled time point. Therefore, LDL-C values missing during the on-treatment period (eg, samples obtained out-side the specified window, no blood sample available although visit was performed, etc.) should be considered "Missing At Random" and imputed based on other on-treatment measurements.
- Patients who stopped taking their study treatment no longer benefited from it after discontinuation, and thus tended to have LDL-C values returning to baseline. Therefore, LDL-C values missing more than 21 days after treatment discontinuation should be imputed based on patient's own baseline value.

For patients who permanently discontinued the treatment due to the COVID-19 pandemic, missing post-treatment data will be considered "Missing at Random" and imputed based on other on-treatment measurements in the same treatment group.

Missing LDL-C values will be imputed 100 times to generate 100 complete data sets. The percent change from baseline to Week 24 will be derived from observed and imputed LDL-C at this time point. The completed data sets will be analyzed using an ANCOVA model, with unequal variances by treatment group (except if convergence issue), with treatment group (alirocumab, placebo) and randomization strata (previous participation [yes or no] to DFI14223 study, baseline body weight [<50 or \geq 50 kg]) as fixed effects, and the baseline LDL-C value as continuous covariate. The results from the 100 analyses will be combined using Rubin's formulae (8).

For the Q4W dosing regimen cohort, the same approach will be taken with the following differences:

- The on-treatment period will be defined as the time period from the first IMP injection up to the day of the last double-blind injection +35 days for patients with a last double-blind injection before the switch to Q2W regimen (actual of sham), +21 days otherwise.
- The ANCOVA model will include treatment group (alirocumab, placebo) and randomization strata (baseline body weight [<50 or ≥50 kg]) as fixed effects, and the baseline LDL-C value as continuous covariate.

2.4.4.1.5 Sensitivity to the impact of COVID-19

To estimate what would have been the treatment effect had the COVID-19 pandemic not occurred, the MMRM model used for the primary analysis will be executed on the population without trial impact/disruption due to COVID-19 (See definition in Section 2.3.6).

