1.1 STUDY DESIGN AND RANDOMIZATION

This study is a randomized, 24-week double-blind, placebo-controlled, parallel-group, multinational, multi-center study followed by an open-label treatment period of 80 weeks.

Approximately 150 children and adolescents 8 to 17 years of age with heterozygous familial hypercholesterolemia (heFH) and low-density lipoprotein cholesterol (LDL-C) \geq 130 mg/dL (3.37 mmol/L) at the screening visit, despite stable lipid modifying therapies (LMTs), are randomized to alirocumab or placebo using a 2:1 ratio (alirocumab: placebo). Two dosing regimens, administration every 2 weeks (Q2W) and every 4 weeks (Q4W), will be evaluated with approximately 75 patients in each dosing regimen cohort. Recruitment in the Q4W dosing regimen cohort started once recruitment in the Q2W dosing regimen cohort was completed and the protocol amendment was approved.

A Flow Mediated Dilation (FMD) exploratory sub-study is also planned to involve a subset of 30-39 patients at selected sites.

Note: Patients who had previously participated in the DFI14223 study and had received alirocumab administration during the open-label extension of the DFI14223 study required a wash-out period of at least 10 weeks between the last injection of alirocumab and the screening lipid assessment at the entry of the screening period. However, as these patients had already met the LDL-C requirement of at least 130 mg/dL (3.37 mmol/L) when they were screened for the DFI14223 study, they were not excluded based on the LDL-C value obtained during the screening for the EFC14643 study.

Randomization is stratified according to previous participation (yes or no) in the Phase 2 DFI14223 study and baseline body weight (BW) (<50 or ≥ 50 kg).

The study is comprised of 4 periods as described below:

- A run-in period (if needed) up to 4 weeks (+2 days) in duration.
- A screening period up to 2 weeks (+5 days) in duration.
- A 24-week double-blind treatment period.
- A 80-week open-label treatment period.

The total study duration may be up to 110 weeks (+7 days).

Double-blind treatment period:

Two dosing regimens will be evaluated, Q2W and Q4W. Patients will be included in them in a sequential manner, ie, the first half of the patients in the Q2W dosing regimen cohort then the second half of patients in the Q4W dosing regimen cohort. Patients will be blinded to study treatment and randomized to either alirocumab or placebo using a 2:1 ratio for each dosing regimen cohort.

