1.6 STATISTICAL MODIFICATIONS MADE IN THE STATISTICAL ANALYSIS PLAN

Changes already incorporated in a protocol amendment are listed in Table 2. The statistical analysis plan history table below gives the timing, rationale, and key details for major changes to the statistical analysis features in this amended version of the statistical analysis plan (version 2) compared to the initial version (version 1) of 8 January 2021.

SAP version number	Date approved	Rationale	Description of statistical changes
2	This version	Per protocol, safety assessments (laboratory data, vital signs etc) at Week 24 are measured on the same day as the administration of first open- label injection (just before)	For patients proceeding into the open-label period, the double-blind TEAE period is truncated at the first open-label injection and not the day before (Section 2.1.4)
2	This version	As per regulatory agency's feedback	Unequal variances by treatment group will be implemented for ANCOVA analyses (Section 2.4.4.1.4, Section 2.4.4.4 and Section 2.4.5.7). Consistently, a correlation matrix by treatment group to model within- patients error will be used for the MMRM models (Section 2.4.4.1.1)
2	This version	As per regulatory agency's feedback	In the pattern mixture model (Section 2.4.4.1.4), post-treatment missing values for patients who discontinued the treatment due to the COVID- 19 pandemic will be imputed under missing at random assumption, ie. based on on-treatment values in the same treatment group
2	This version	Simplification	Removal of a sensitivity analysis in Section 2.4.4.1.5 as a similar analysis is already included in Section 2.4.4.1.4
2	This version	As per regulatory agency's feedback	Pattern Mixture Model for key secondary continuous efficacy endpoints normally distributed will be implemented (Section 2.4.4.2.1)
2	This version	As per regulatory agency's feedback	For binary efficacy endpoints, in the situation of data dependent case, post-treatment missing values will be considered as failure (except for patients who discontinue due to the COVID-19 pandemic) (Section 2.4.4.2.3)

Table 3 - Statistical analysis plan statistical changes

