2.3.6 Population without trial impact/disruption due to COVID-19

The population without trial impact/disruption due to COVID-19 will be defined as any patient without any of the following:

- Major or critical deviation related to COVID-19
- Permanent treatment discontinuation related to COVID-19
- Permanent study discontinuation related to COVID-19.

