2.4 STATISTICAL METHODS

General rules

Analyses will be performed separately for the double-blind and the OL periods, unless otherwise noted.

Double-blind period

Unless otherwise specified, the analyses will be performed by treatment group (placebo, alirocumab) within each dosing regimen cohort.

In addition, for disposition, populations, demographic/baseline characteristics, safety and other endpoints (refer to Section 2.1.5), analyses will be provided by treatment group (placebo, alirocumab) regardless of the dosing regimen cohorts (pooled across cohorts).

Of note, an Overall column will be displayed for populations, demographics and baseline characteristics.

OL period

The summaries will be displayed according to the treatment group (placebo, alirocumab) received in the double-blind period and Overall within each dosing regimen cohort (dosing regimen initiated at the randomization).

For disposition, populations, demographic/baseline characteristics, safety and other endpoints, analyses will be also provided by treatment group received in the double-blind period regardless of the dosing regimen cohorts, and Overall.

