3 INTERIM ANALYSIS

The analyses will be conducted in 2 steps. The first analysis will not be conducted before completion of the double-blind treatment period. Since analysis of double-blind primary and key secondary efficacy endpoints will have been concluded at the time of the first step analysis described below, no multiplicity adjustment for multiple analyses is needed (see Section 2.4.4.3), and the overall significance level remains at 0.05 for the study.

- First step analysis: Analysis of the completed double-blind treatment period and first step analysis of the open-label treatment period
 - This analysis will be conducted when all patients have been randomized and have at least all their lipid data up to Week 24 analysis window (double-blind period) collected and validated.
 - The efficacy analyses of the double-blind period will consist in the final analysis of the primary and secondary efficacy endpoints (except those measured during open-label period). Analysis of lipid data collected during the OL period will be descriptive.
 - The safety analyses of the double-blind period will not be fully final at the time of this analysis since the double-blind TEAE period will be truncated at the cut-off date for some patients. The safety analyses of the double-blind and open-label treatment periods will be performed on all safety data collected up to the common cut-off date. The common cut-off date is defined as date of the last patient included completed Week 24 visit.
- Final analysis of the open-label treatment period
 - This analysis will be conducted at the end of the study with the data of the open-label treatment period and will consist in the final analysis of the safety and efficacy measures of the open-label treatment period.

Analyses methods and conventions described in the other sections of this SAP will be applied for all analyses as applicable. The following additional rules will apply for analyses performed at first analysis:

- Any lipid assessments within analysis windows up to Week 24 will be taken into account (may include few unscheduled lipid data soon after the cut-off date).
- Open-label period: Patients without end of treatment visit performed at the time of the cutoff date will be considered as ongoing and exposed up to the cut-off date. Therefore:
 - Patients who did not complete treatment period nor prematurely discontinued the study treatment at cut-off date will be analyzed as "ongoing" in the disposition summary.

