4 DATABASE LOCK

As the analysis will be conducted in two-steps, two database locks will be done:

- First database lock (for first step analysis): will include all available data on all randomized patients up to the common cut-off date as defined in Section 3. This database lock is planned to be done approximately 4 weeks after the common cut-off date.
- Final database lock (for final analysis): will include all data of the open-label treatment period, for all patients entered in the OL period. This database lock is planned to be done approximately 4 weeks after last patient last visit.

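### Does the COVID-19 sensitivity analysis wrongly drop patients whose only disruption came after Week 24?

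*SAP*

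**What the plan says.** SAP 2.4.4.1.5 states its aim as "To estimate what would have been the treatment effect had the COVID-19 pandemic not occurred" and, to that end, provides that "the MMRM model used for the primary analysis will be executed on the population without trial impact/disruption due to COVID-19". SAP 2.3.6 defines that set: "The population without trial impact/disruption due to COVID-19 will be defined as any patient without any of the following". It then lists COVID-19-related major or critical deviations, permanent treatment discontinuation and permanent study discontinuation. Neither section gives a period, visit or date.

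The primary MMRM (SAP 2.4.4.1.1) uses only values in the Week 8, 12 and 24 windows. For patients who continue, the Week 24 window closes no later than the first open-label injection (SAP 2.5.4, Table 5 footnote).

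The first lock "will include all available data on all randomized patients up to the common cut-off date as defined in Section 3", and "The common cut-off date is defined as date of the last patient included completed Week 24 visit". On recruitment order, SAP 1.1 says: "Recruitment in the Q4W dosing regimen cohort started once recruitment in the Q2W dosing regimen cohort was completed".

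The general rule in SAP 2.4 is: "Analyses will be performed separately for the double-blind and the OL periods, unless otherwise noted".

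**The concern.** A patient randomised early in the Q2W cohort may have finished the double-blind period undisturbed and then stopped open-label treatment because of the pandemic. If that happened before the common cut-off, the patient carries one of the three listed events. On a literal reading the patient leaves the sensitivity MMRM, although every LDL-C value it would have used was collected before the event.

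The silence of SAP 2.3.6 stands out because its neighbours are explicit. The antibody and PK populations (SAP 2.3.3 and 2.3.4) both stop at Week 24, early termination or the first open-label injection. Two programmers could in principle build different populations, and the needless losses would fall mainly on the Q2W comparison.

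There is also a second strand. The stated target is the effect in a world without the pandemic, but the method selects patients on events after randomisation. The two agree only if the excluded patients resemble the retained ones within arm, given the model covariates. SAP 2.4.4.1.5 does not state that assumption.

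**Working it through.** **Can open-label events be in the first lock?** Yes. Q2W recruitment was complete before Q4W recruitment began, and the cut-off is the last included patient's Week 24 visit. A Q2W patient who continued has open-label follow-up before the cut-off roughly equal to the gap between that patient's randomisation and the last patient's. SAP 3 drops discontinuations after the cut-off but not earlier open-label ones.

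**Which reading do the documents favour?**

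- SAP 2.4 makes analyses period-specific unless otherwise noted. The analysis in 2.4.4.1.5 belongs to the double-blind period.
- SAP 2.2 summarises deviations in the randomised population for the double-blind period and in the open-label population for the open-label period. It applies the COVID-19 split to that description.
- SAP 2.4.3 does the same for exposure and compliance, which are also reported by period.

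A COVID-19 status tied to the period being analysed fits all three. A single lifetime flag is possible on the words of 2.3.6 alone, but it would classify double-blind summaries by events that had not yet happened.

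**What would the literal reading cost?** Inputs from SAP 1.3: difference 30 points, SD 25, two-sided alpha 0.025 per comparison, 2:1 allocation, 50 and 25 patients per cohort.

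Formulas:

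- SE = 25 × √(1/nA + 1/nP)
- half-width of the 97.5% CI = t(0.9875; nA + nP − 2) × SE
- power from the noncentral t with noncentrality 30/SE

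The plan's own figure first. At 30:15, SE = 25 × √(1/30 + 1/15) = 7.91, the noncentrality is 30/7.91 = 3.79 on 43 degrees of freedom, and power is 92.5%. The SAP states 92%, so the method reproduces it.

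The documents contain no COVID-19 counts, so the excluded shares below are assumptions.

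| Excluded (assumed) | nA:nP | SE | Half-width | Ratio to full cohort | Power |
|---|---|---|---|---|---|
| 0% | 50:25 | 6.12 | 14.01 | 1.00 | 99.5% |
| about 5% | 47:24 | 6.27 | 14.37 | 1.03 | 99.3% |
| about 10% | 45:22 | 6.50 | 14.92 | 1.06 | 98.9% |
| 20% | 40:20 | 6.85 | 15.75 | 1.12 | 98.0% |
| 40% | 30:15 | 7.91 | 18.36 | 1.31 | 92.5% |

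The last row is the plan's own minimum sample size: losing 40% of a cohort would only bring the sensitivity analysis back to the size on which the trial was powered.

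Two limits apply. The shares are total exclusions, and only the part due to open-label-only events would be avoidable, so each row is an upper bound on the cost of the literal reading at that share. The calculation is an unadjusted two-sample comparison, whereas the analysis is a baseline-adjusted MMRM. The ratios are therefore a better guide than the absolute half-widths.

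**The case for a change.** The strongest reply is that a pre-specified analysis should have one reproducible population. SAP 2.4 separates analyses, not population membership, and SAP 2.2 sends both periods to the same definition. Since 2.3.3 and 2.3.4 show that the authors wrote a period limit when they wanted one, its absence from 2.3.6 might be deliberate. That much stands: the text does not settle the matter by itself, and a clarifying phrase would do no harm if well placed.

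Placement matters, though. A double-blind limit in 2.3.6 would empty the open-label COVID-19 summaries of open-label events, because they use the same definition. A cap at the end of the Week 24 window (day 182) could misfire too. Protocol Appendix K allows remote visit windows to be extended in an emergency, so a patient whose Week 24 assessment was delayed by the pandemic might be dated outside the cap and counted as undisrupted.

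The mismatch between aim and method is real but changes no result. SAP 2.4.4.1.1 states the missing-at-random assumption for the MMRM. The pattern mixture model in 2.4.4.1.4 excludes nobody because of COVID-19 and says explicitly that missing values after a COVID-19 treatment discontinuation are imputed as missing at random. A reader who distrusts the subset analysis has that one beside it. Setting values to missing only after COVID-19 treatment discontinuation would largely repeat it, and would ignore the deviations that 2.3.6 lists first.

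The SAP 1.6 entry "Removal of a sensitivity analysis in Section 2.4.4.1.5 as a similar analysis is already included in Section 2.4.4.1.4" settles nothing here, since it concerns an analysis no longer in the plan.

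**Conclusion.** No change to the plan follows. SAP 2.3.6 leaves out a detail that the surrounding sections let an analyst fill sensibly: for a double-blind analysis, count COVID-19 events arising in the double-blind period, including any that delayed or prevented the Week 24 assessment.

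If the literal reading were used instead, the loss would be some precision in one sensitivity analysis, mainly in the Q2W cohort. It amounts to about 3% to 12% on the confidence interval width at assumed exclusions of 5% to 20%, with power of at least 98%. The true share is unknown. Bias between arms from open-label-only events is not a strong worry, because all patients receive alirocumab in that period (SAP 1.1). The primary ITT analysis, the 0.025 level per comparison and the key secondary hierarchy do not use this population at all.

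The conclusion rests on the SAP 1.3 planning values (SD 25, difference 30) and on COVID-19 exclusions not greatly exceeding the range shown. The result is best read as the effect in patients without COVID-19 disruption during the double-blind period.

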2.3.1.1 Intent-to-treat population

The ITT population is defined as all randomized patients.

Patients in the ITT population will be analyzed according to the treatment group allocated by randomization (ie, as-randomized treatment group).

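### The COVID-19 sensitivity analysis aims at the effect without the pandemic but drops whole randomised patients by mostly post-randomisation events, so it answers a different question and discards usable LDL-C values

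*SAP*

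**What the plan says.** SAP 2.4.4.1.5 gives the aim as follows: "To estimate what would have been the treatment effect had the COVID-19 pandemic not occurred". The method is that "the MMRM model used for the primary analysis will be executed on the population without trial impact/disruption due to COVID-19".

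SAP 2.3.6 defines that set: "The population without trial impact/disruption due to COVID-19 will be defined as any patient without any of the following". The three triggers are:
- "Major or critical deviation related to COVID-19"
- "Permanent treatment discontinuation related to COVID-19"
- "Permanent study discontinuation related to COVID-19"

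The rule works on patients, not on visits or values. It is not limited to the double-blind period or to deviations that touch LDL-C.

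The primary analysis (SAP 2.4.4.1.1) uses the ITT population, where "The ITT population is defined as all randomized patients". It takes every LDL-C value in the Week 8 to Week 24 windows and relies on missing at random for the rest.

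SAP 2.4.4.1.4 also treats COVID-19 separately, inside the pattern mixture model: "For patients who permanently discontinued the treatment due to the COVID-19 pandemic, missing post-treatment data will be considered" missing at random and imputed from on-treatment values in the same arm.

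**The concern.** The stated target is a hypothetical effect in the randomised patients. The method estimates the effect in patients who escaped disruption. Two of the three triggers can only occur after randomisation, and protocol deviations mostly do, so membership of the subset is decided largely by post-baseline events.

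The exclusion is also wasteful. A patient disrupted at Week 20 loses good Week 8 and Week 12 values. As worded, a patient with a COVID-19 deviation in the open-label period, after a valid Week 24 sample, is dropped as well.

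An external cause does not make exclusion random. Protocol Appendix K leaves continuation on treatment in an emergency to the investigator's case-by-case judgement of individual benefit and risk, so patient factors can influence who is excluded. If the primary and COVID-19 results differed, a reader could not separate a pandemic effect from selection.

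**Working it through.** **Inputs.** From SAP 1.3: 50 alirocumab and 25 placebo patients planned per cohort, SD 25 points, difference 30 points, two-sided alpha 0.025. Not in the documents and therefore assumed: the share affected (10 to 40%, equal in both arms) and the Week 12 to Week 24 correlation r (0.5 to 0.8).

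**The plan's own figure.** SAP 1.3 states 92% power with 30 versus 15. A two-sample t-test (noncentral t, 43 df) gives 92.5%, so the figure reproduces. The documents give no number for the COVID-19 analysis itself.

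**Precision.** Let m_c and m_t be the placebo and alirocumab patients not affected.
- Whole-patient exclusion: SE = 25 × sqrt(1/m_c + 1/m_t).
- Everyone kept, with only affected Week 24 values missing at random: SE = 25 × sqrt[(1 − r²)(1/m_c + 1/m_t) + r²(1/25 + 1/50)].

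Example at 20% affected (m_c = 20, m_t = 40):
- Exclusion: 25 × sqrt(0.075) = 6.85.
- Kept, r = 0.5: 25 × sqrt(0.75 × 0.075 + 0.25 × 0.06) = 6.67.
- Kept, r = 0.8: 25 × sqrt(0.36 × 0.075 + 0.64 × 0.06) = 6.39.

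With nobody affected, the SE is 25 × sqrt(0.06) = 6.12.

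| Affected | Left (placebo : alirocumab) | SE, excluded | SE, kept (r 0.5 to 0.8) | Ratio | Power, excluded |
|---|---|---|---|---|---|
| 10% | 22.5 : 45 | 6.45 | 6.37 to 6.24 | 1.01 to 1.03 | 99.0% |
| 20% | 20 : 40 | 6.85 | 6.67 to 6.39 | 1.03 to 1.07 | 98.0% |
| 30% | 17.5 : 35 | 7.32 | 7.04 to 6.58 | 1.04 to 1.11 | 96.0% |
| 40% | 15 : 30 | 7.91 | 7.50 to 6.82 | 1.05 to 1.16 | 92.5% |

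These ratios suppose that each affected patient loses the Week 24 value and keeps Week 12. If a deviation left Week 24 valid, keeping the patient gains more; if Week 12 is also unusable, it gains less.

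**Bias.** Week 12 and Week 24 residuals were simulated as bivariate normal (SD 25; r = 0.5, 0.7, 0.8; two million draws per scenario). Exclusion depended on the Week 12 response in the alirocumab arm only. The probabilities for better versus worse responders were 10% versus 20%, 10% versus 30%, and 5% versus 40%. Whole-patient exclusion moved the difference by −0.6 to −3.6 points, in favour of alirocumab. Keeping Week 12 and using missing at random left about 0. When exclusion is unrelated to response and arm, the bias is 0 and only precision is lost.

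**The case against.** The case for leaving the plan alone has several parts.

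- **It is only a sensitivity analysis.** This stands. The primary MMRM on all randomised patients, the Bonferroni split and the hierarchy do not depend on it. Even 40% exclusion leaves 30 versus 15, the size for which SAP 1.3 states 92% power.
- **Strongly arm-related exclusion is unlikely.** This largely stands. Treatment and post-randomisation lipids are blinded to sites (Protocol 8.3.1 and 8.3.1.2), and the cause is external. The −3.6-point case needs an extreme pattern in one arm, against a planned effect of 30. A reader might infer that the analysis is biased; the documents support only that the subset is no longer protected by randomisation.
- **Few values may be lost.** This is possible. Appendix K allows remote LDL-C sampling and wider remote visit windows. But where values were obtained, removing the patient is harder to justify.
- **The pattern mixture model already keeps everyone.** This is partly right. It handles only missing values after COVID-19 treatment discontinuation, by multiple imputation with ANCOVA. It keeps observed values, does not address COVID-19 deviations, and imputes other discontinuers around their own baseline. It therefore does not isolate the pandemic, and it would be wrong to read it as already doing what is proposed here.

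Two further inferences go too far. One is that exclusion costs 12 to 29% in standard error at 20 to 40% affected (1/sqrt(0.8) = 1.118; 1/sqrt(0.6) = 1.291). That compares with no disruption at all, whereas affected Week 24 values would be missing under the alternative too. The other is that the Q4W cohort is the more exposed. It enrolled second, which makes this plausible, but the documents do not give enrolment dates relative to the pandemic.

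**Conclusion.** The mismatch is clear from SAP 2.4.4.1.5 and 2.3.6 read together: the aim is hypothetical and concerns the randomised patients, while the analysis set is a subset formed largely after randomisation. Valid LDL-C values are discarded although the primary model could use them.

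The size is modest. The standard error is about 1 to 16% larger than with retention, under assumed shares of 10 to 40% and assumed correlations of 0.5 to 0.8. Bias may be zero; it reached 3.6 points only in the most extreme scenario tried. No stated figure in the plan is wrong, and the primary conclusion is not at risk. This is a lower-severity point, worth making because the analysis as written does not answer its own question and the remedy is inexpensive.

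**What to change.** In SAP 2.4.4.1.5, for each cohort, run the primary MMRM on the full ITT population and set to missing only double-blind LDL-C values that are either:
- collected after a COVID-19-related permanent treatment discontinuation, beyond the SAP's own on-treatment window (last injection +21 days, or +35 days for Q4W patients who stopped before the Week 12 switch); or
- dated on or after a COVID-19 major or critical deviation judged, before unblinding, to affect that value.

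Keep all other values, ignore events after the Week 24 sample, and report the number of affected patients by arm. Retain the SAP 2.3.6 subset model as a supplementary analysis, without describing it as the effect had the pandemic not occurred.

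**Cost.** SAP wording, one value-level data flag and one extra model run per cohort. COVID-19 deviations already have to be identified to build the SAP 2.3.6 population, but the documents do not show that they are linked to individual LDL-C samples. A blinded review must date them and link them to visits. The result relies on missing at random for the values removed, and the SAP should say so.
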